6.2 Trial Population

The study participants will be recruited from patients admitted to Toronto Western Hospital for elective posterior cervical spine surgery requiring motor evoked potential monitoring as per the admitting surgeon.

Inclusion criteria

- All adult patients aged 18-80 years with ASA class I-III undergoing cervical spine surgery in the prone position with motor evoked potential monitoring.
- Operation time greater than 3 hours

Exclusion criteria

- Allergy to propofol or documented egg allergy
- Known allergy to sugammadex
- Severe renal dysfunction (EGFR<30)
- British Research Medical Council (BRMC) motor grading <3 in any peripheral muscle group pre-operatively. This is inability to move the muscle group against gravity.
- Surgical requirement of strict muscle relaxation for surgical exposure
- Lack of informed consent
- Pregnancy
- Loss of MEPs signals during washout period (or intraoperative spinal cord injury resulting in irreversible loss of MEP)

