The crossover arm of the trial is to enable patients to function as their own control group. During surgical closure patient will remain on a total intravenous anaesthesia (propofol and remifentanil). When the patient returns to a train of four count of 2 or more on peripheral nerve monitor repeat motor evoked potentials will then be recorded and

patients will receive the alternate drug to the one received in the initial arm of the trial.

The purpose of this study is to determine the increase in amplitude of the motor evoked potentials when residual neuromuscular blockade is reversed with sugammadex or placebo.

4. Hypothesis

We hypothesize that reversal of neuromuscular blockade by sugammadex will increase the amplitude of motor evoked potentials compared with placebo.

5. Significance of the study

Facilitating increased amplitudes of MEPS via reversal of residual neuromuscular blockade will enable increased accuracy of monitoring.

Providing the option of reversal of neuromuscular blockade will allow MEPs to be monitored during patient positioning to prevent placing them in a neurologically compromising position.

6. Methods

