6.1 Research Design

This is a prospective, single centre, triple blinded randomised controlled cross-over trial. Patients who are scheduled for an elective posterior cervical spine procedure in prone position and require motor evoked potential monitoring (MEPs) will be included. Patients will be randomised to assign to one of the following treatment sequences: sugammadex followed by placebo, or vice versa. The primary outcome is the change of MEP amplitude of the first dorsal interossei from baseline 3 minutes after administration of the allocated intervention. The patients, anesthesiologists and neurophysiologists (outcome assessor) will be blinded for the allocated intervention group.

The first study intervention will be performed after the patients are positioned in prone with a train of four count of 2 and satisfactory baseline motor evoked potentials have been recorded. This will likely occur during or just prior to surgical exposure.

The second study intervention will be performed during surgical closure. This will be once the surgeons have completed their use of motor evoked potentials and the patient remains on total intravenous anaesthesia (propofol and remifentanil). A minimum washout period of 100 min after the last bolus dose of rocuronium (equivalent to 5 half lives) is required and the completeness of washout will be confirmed with no residual tetanus fade, fade on train of four (or fading in double burst stimulation) on a peripheral nerve stimulator. The operative time

of posterior cervical spine procedure is usually around 3 hours and should allow complete washout of rocuronium. After the preconditions are achieved on peripheral nerve stimulator or the direct train of four monitor, the second intervention (either sugammadex or placebo) will be administered.

On each occasion the increase in amplitude of the motor evoked potential of both upper and lower limbs will be assessed at 3,6,9,12 and 15 minutes post intervention.

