6.3 Recruitment

All patients who are admitted to Toronto Western Hospital and satisfy the above criteria will be considered for enrolment into the study. Informed consent will be sought as detailed in section 12. A record will be kept of all eligible patients who are not enrolled and reasons for non-enrolment.

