6.5 Allocation Concealment

Sequentially numbered, opaque, sealed envelopes will be used for allocation schedules and individual assignments. The study envelope will be opened at the beginning of each case by a trained research assistant and the reversal drugs will be prepared.

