7.2 Study Protocol

Patients should undergo peripheral nerve monitoring following the induction via a peripheral nerve stimulator and by a direct train of four monitor by the neurophysiologists. The train of four should be assessed on peripheral nerve stimulator and on the neurophysiology monitoring prior to turning the patient prone. If the patient has two or more twitches on either monitoring they should be given 0.1mg/kg rocuronium prior to positioning prone.

Once the patient is in their final position for surgery the anaesthetic will be changed to a total intravenous anaesthetic (TIVA) with propofol and remifentanil titrated to entropy of 40-60. The volatile anaesthesia has to be washed out with high flows of 10L/min until end tidal desflurane is less than or equal to 0.2.

When the above conditions are met the train of four count (TOFC) will be checked by the anaesthesiologist. When the TOFC is 2 or more the baseline motor evoked potentials (bMEPs) will be performed.

Following the bMEPs the anaesthesiologist will administer the reversal drug (either sugammadex 2mg/kg in 10 ml syringe or matching placebo). This time must be strictly recorded, as it is the time that has elapsed since the induction dose of muscle relaxant. The neurophysiologist will perform and record MEPS at 3,6 and 9 minutes post reversal dose. The following parameters will continuously be monitored during the study period: TOFC, Entropy, BP, HR, CO2,

peak airway pressures, anaesthetic infusion rates, temperature and oxygen saturation. If the testing occurs during surgical exposure it is important to ask the surgeons to make a very brief pause to allow the motor testing to be performed and to check the entropy at the same time.

Following surgery commencement there will be a surgical grading of the relaxation of the surgical field once exposure attained and collection of surgeon stated observation of patient movement.

The operative time of posterior cervical spine procedure is usually around 3 hours and should allow for complete washout of rocuronium. A minimum washout period of 100 min after the last bolus dose of rocuronium (equivalent to 5 half-lives) is required and the completeness of washout will be confirmed with no residual tetanus fade, no fade on train of four (or fading in double burst stimulation) on a peripheral nerve stimulator.

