9.1 Data Collection

The following data will be collected (see attached Data Collection Form):

Administrative Data

Screening log- detailing numbers of potential participants screened for inclusion and reasons for exclusion and numbers actually recruited.

Demographic data

Age, sex, height, weight, American Society of Anaesthesiologists physical class (ASA)

Study Data

Baseline data as detailed in section 8
Outcome data as defined in section 8

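### Loss of MEP signal between the two periods is listed as an exclusion criterion, although it follows allocation, the first dose and the period-1 primary measurement, and section 11 has no rule that keeps the period-1 data

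*Combined protocol and SAP*

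**What the plan says.** All of these places are in the combined protocol and SAP.

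- **Section 6.2** gives, as the last exclusion criterion, "Loss of MEPs signals during washout period (or intraoperative spinal cord injury resulting in irreversible loss of MEP". It stands beside items that can be checked before surgery, such as allergy, renal function and pregnancy.
- **Section 6.5**, on timing of allocation: "The study envelope will be opened at the beginning of each case".
- **Section 7.2**, on the first period: "Following the bMEPs the anaesthesiologist will administer the reversal drug", and then "The neurophysiologist will perform and record MEPS at 3,6 and 9 minutes post reversal dose".
- **Section 6.1** defines the endpoint: "The primary outcome is the change of MEP amplitude of the first dorsal interossei from baseline 3 minutes after administration of the allocated intervention". It places the second dose at surgical closure, at least 100 minutes after the last rocuronium bolus.
- **The crossover rationale** (before section 4) gives the purpose of the second period: "The crossover arm of the trial is to enable patients to function as their own control group".
- **Records of patients left out.** Section 6.3 states "A record will be kept of all eligible patients who are not enrolled and reasons for non-enrolment". Section 9.1 describes a screening log "detailing numbers of potential participants screened for inclusion and reasons for exclusion and numbers actually recruited".
- **Section 10.2** requires 30 patients and enrols 40 to allow for 15-25% drop-out.
- **Section 11** compares amplitudes with a Mann-Whitney U test. It names no analysis population and does not say how a patient with only one period is handled.

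**The concern.** An exclusion criterion decides who belongs to the trial population. This one cannot be assessed until the operation is under way, when the sequence is already fixed. A patient who loses signal between the periods has been randomised and dosed and has supplied a period-1 primary value. Excluding that patient restricts the analysis to people whose MEPs survived to closure, which is selection after allocation on something tied to the endpoint.

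Three things are at stake:

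- a defined randomised population;
- an account of losses by sequence, since the two records described cover patients not enrolled and not those lost after allocation;
- possible bias, if the chance of loss depends on the first drug through the period-1 value.

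Because section 11 is silent, whether these patients count could be decided after their data are seen.

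**Working it through.** **1. Order of events.** Envelope opened at the start of the case (6.5); baseline MEPs, then first dose (7.2); 3-minute primary measurement (6.1, 7.2); surgery and washout; second dose at closure (6.1). A loss between the periods therefore follows the first three steps. There is an exception. The washout clock runs from the last rocuronium bolus, which may precede the first study dose, and a cord injury could also occur before that dose. Not every event under the criterion is post-dose.

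**2. The plan's sample size.** Inputs from section 10.2: within-patient SD 1600, difference 1200, two-sided 0.05, power 80%.

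- Normal approximation: N = 2 × [1600 × (1.960 + 0.842) / 1200]² = 27.9, so 28.
- t-based, SD of the paired difference 1600 × √2 = 2263, N − 2 degrees of freedom: 30 pairs give 80.1%. The plan's 30 is reproduced.
- Drop-out: 30 / (1 − 0.25) = 40, also reproduced.

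**3. Power after losses.** Losing 40 × 0.15 = 6 leaves 34 pairs and 85.0% power. Losing 40 × 0.25 = 10 leaves 30 pairs and 80.1%. The allowance covers losses up to the planned 25%.

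**4. Bias of a complete-pair contrast.** The documents give neither a rate of MEP loss nor a within-patient correlation, so these are assumptions. Model: value = patient + 1200 × treatment + error, within-patient SD 1600. Loss after period 1 is logistic, more likely with a lower period-1 value, with slope 0.5, 1 or 2 per SD of that value. Bias in microV over the three slopes, with simulation error of a few microV:

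| Correlation | 5% lost | 15% lost | 25% lost |
|---|---|---|---|
| 0 | −8 to −58 | −18 to −120 | −27 to −160 |
| 0.5 | −1 to −28 | −8 to −59 | −10 to −79 |
| 0.75 | −2 to −15 | −5 to −31 | −6 to −41 |

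- The −160 becomes about −150 if the slope is scaled by the SD across both treatments rather than within one.
- Relative size: 79 / 1200 = 6.6%; 160 / 1200 = 13.3%.
- Loss then differs by sequence. At correlation 0.5, slope 2 and 15% overall, it is about 10.5% when sugammadex is first and 19.5% when placebo is first.
- If loss depends only on the patient's stable level, or on the period-1 value with the drug effect removed, loss is equal by sequence and bias is 0 within simulation error.

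**5. Keeping period-1-only patients.** In the same scenarios, a random-patient mixed model fitted to trials of 40 was within 13 microV of 1200 (simulation error 6 to 7). The simulated loss depends only on the observed period-1 value, which is the condition under which such a model is valid, so this result is largely built in.

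The variance reduction is Vc / (Vc + V1), with Vc = 2(1 − ρ)/n for n pairs and V1 = 2/m for m period-1-only patients per sequence. For n = 34, m = 3, ρ = 0.5: Vc = 0.0294, V1 = 0.6667, reduction 4.2%.

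| n pairs, m per sequence | ρ = 0 | ρ = 0.5 | ρ = 0.75 |
|---|---|---|---|
| 38, 1 | 2.6% | 1.3% | 0.7% |
| 34, 3 | 8.1% | 4.2% | 2.2% |
| 30, 5 | 14.3% | 7.7% | 4.0% |

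The last two rows treat every planned drop-out as a period-1-only patient, so they are upper cases.

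**The case against.** The strongest defence is that an event during washout cannot be a screening rule. On that view the line is a condition for entering period 2, put under the wrong heading, and the drop-out allowance shows that losses after randomisation were foreseen. This reading is plausible. It does not close the gap: the allowance sets a number and not a rule, and nothing in section 11 says what happens to the period-1 value.

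The second objection is that the bias needs a mechanism the documents do not describe. No text links MEP loss to the first drug, and the washout and recovery conditions are meant to remove the difference in blockade before period 2. This stands. The documents neither support nor exclude dependence on the drug-affected value, so zero bias is as consistent with them as the non-zero figures.

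Third, even 79 microV is only about 0.2 of the standard error: 2263 / √34 = 388 and 2263 / √30 = 413. That also stands, and it limits the weight of the point.

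Fourth, the mixed model estimates the effect as if MEPs had persisted, which is debatable after irreversible loss. This is a fair limitation. It should be stated in the plan, and it is why complete pairs belong in a sensitivity analysis.

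A reader might also infer that period-1 or side-effect data will be deleted, or that the Mann-Whitney test itself shuts out single-period patients. The documents say neither. They are silent on how such patients enter.

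**Conclusion.** The point holds as a defect of definition. Section 6.2 places an event that follows allocation and dosing among the eligibility rules, and section 11 has no analysis set or rule that keeps the period-1 data. The wording and the omission are certain; the size of any effect is not.

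Bias in a complete-pair contrast is about 0 unless loss depends on the drug-affected period-1 value. If it does, it understates the effect by at most about 80 of 1200 microV at an assumed correlation of 0.5 to 0.75.

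A reader might take 13% as the expected bias. That figure of about 150 to 160 microV requires correlation 0, 25% loss with every drop-out an MEP loss, and the steepest slope together, so it is a worst case. Nor is the trial underpowered on this account: 30 complete pairs still give 80%. The change should be made because it is cheap and fixes the analysed population in advance, not because the result is likely to be far off.

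**What to change.** - **Section 6.2:** move the item out of the exclusion criteria and list it as a reason for missing period-2 data.
- **Section 11, analysis set:** define the primary set as all randomised patients given a first dose.
- **Section 11, primary analysis:** replace the unpaired Mann-Whitney test with a mixed model for the 3-minute change in microV, with treatment and period fixed and patient random. Pairs are then used as pairs and period-1-only patients contribute.
- **Sensitivity analyses:** complete pairs. Any log-ratio analysis also belongs here, because it changes the scale on which the trial was sized.
- **Reporting:** give MEP losses by sequence, and show losses before the first dose in the participant flow with the reason.

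**Cost:** no new data or visits; one line moves, one definition is added and the amplitude analysis changes. The model brings a distributional assumption, and 2000 ± 1600 microV suggests skew. It treats missing period-2 values as missing at random given period 1, so the estimate is as if MEPs had persisted. The plan should state both.

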6.3 Recruitment

All patients who are admitted to Toronto Western Hospital and satisfy the above criteria will be considered for enrolment into the study. Informed consent will be sought as detailed in section 12. A record will be kept of all eligible patients who are not enrolled and reasons for non-enrolment.

6.4 Randomisation Method

Enrolled patients will be randomised according to a computer based, permuted block randomisation method, with a 1:1 allocation ratio and a variable block size of 4-6.

6.5 Allocation Concealment

Sequentially numbered, opaque, sealed envelopes will be used for allocation schedules and individual assignments. The study envelope will be opened at the beginning of each case by a trained research assistant and the reversal drugs will be prepared.

6.6 Blinding

This is a randomised blinded study where the administering anaesthetist, surgeon and neurophysiologists will be blinded to the intervention. The study patients will receive a 10ml syringe containing either sugammadex or placebo (saline 0.9%) to be administered in a 1mls per 10kg basis (up to 100kg). Further, a blinded research assistant will perform assessment, data collection, and analysis of neurophysiology data attained.

7. Protocol

7.1 Standard Perioperative Care

Routine standard preparation of the patients will be carried out as per our institutional standard for patients undergoing spine surgery. All routine physiological monitoring (e.g. ECG, invasive arterial blood pressure, SpO₂, end tidal CO₂, temperature and depth of anaesthesia monitoring) will be performed.

The induction of anaesthesia will be performed with propofol (2-5 mg/kg), fentanyl (2-3mcg/kg) and rocuronium (0.6mg/kg) following calibration of the peripheral nerve stimulator. The patient's trachea will be intubated once the peripheral nerve stimulator shows no twitches. The time of induction and rocuronium dose must be strictly recorded. After tracheal intubation the lungs will be ventilated to maintain a PaCO₂ between 33-35mmHg. Maintenance of anaesthesia will be with desflurane inhalational anaesthesia titrated to entropy 40-60 until final operative position is achieved.

Hemodynamic management will target a mean arterial pressure (MAP) >70 mmHg using standard inotropes and/or vasopressors (e.g. phenylephrine and ephedrine)

Prophylactic antibiotics and dexamethasone will be administered as per surgical request and institutional practice. Analgesia should be administered with fentanyl in additional 25mcg boluses up to the completion of surgical exposure and then left to clinical judgement

there-onwards. Anti-emetics should be administered as per the anaesthesiologist practice.

Patients should undergo peripheral nerve monitoring following the induction via a peripheral nerve stimulator and by a direct train of four monitor by the neurophysiologists.

On completion of the cross over arm of the trial, the patient may be changed to volatile anaesthesia as per institutional practice and extubated based on anaesthesiologist clinical judgement. Use of a nerve stimulator to assess the train of four count with reversal of residual neuromuscular blockade with neostigmine and glycopyrrolate if deemed appropriate at the end of the case is recommended.

Post-operative anaesthetic care will occur in the recovery room as per standard practice in terms of oxygen therapy, monitoring and assessment of neurological status, pain, nausea, vomiting and degree of sedation. Fentanyl 25mcg iv will be administered every 5 mins up to a maximum of 200mcg to maintain a Numeric Pain Score <4 of 10. Morphine or Hydromorphone will be used for additional analgesia after fentanyl. Nausea may be managed with dimenhydrinate 25-50mg IV and ondansetron 4m IV.

7.2 Study Protocol

Patients should undergo peripheral nerve monitoring following the induction via a peripheral nerve stimulator and by a direct train of four monitor by the neurophysiologists. The train of four should be assessed on peripheral nerve stimulator and on the neurophysiology monitoring prior to turning the patient prone. If the patient has two or more twitches on either monitoring they should be given 0.1mg/kg rocuronium prior to positioning prone.

Once the patient is in their final position for surgery the anaesthetic will be changed to a total intravenous anaesthetic (TIVA) with propofol and remifentanil titrated to entropy of 40-60. The volatile anaesthesia has to be washed out with high flows of 10L/min until end tidal desflurane is less than or equal to 0.2.

When the above conditions are met the train of four count (TOFC) will be checked by the anaesthesiologist. When the TOFC is 2 or more the baseline motor evoked potentials (bMEPs) will be performed.

Following the bMEPs the anaesthesiologist will administer the reversal drug (either sugammadex 2mg/kg in 10 ml syringe or matching placebo). This time must be strictly recorded, as it is the time that has elapsed since the induction dose of muscle relaxant. The neurophysiologist will perform and record MEPS at 3,6 and 9 minutes post reversal dose. The following parameters will continuously be monitored during the study period: TOFC, Entropy, BP, HR, CO2,

peak airway pressures, anaesthetic infusion rates, temperature and oxygen saturation. If the testing occurs during surgical exposure it is important to ask the surgeons to make a very brief pause to allow the motor testing to be performed and to check the entropy at the same time.

Following surgery commencement there will be a surgical grading of the relaxation of the surgical field once exposure attained and collection of surgeon stated observation of patient movement.

The operative time of posterior cervical spine procedure is usually around 3 hours and should allow for complete washout of rocuronium. A minimum washout period of 100 min after the last bolus dose of rocuronium (equivalent to 5 half-lives) is required and the completeness of washout will be confirmed with no residual tetanus fade, no fade on train of four (or fading in double burst stimulation) on a peripheral nerve stimulator.

The crossover arm of the trial will occur during surgical closure at the end of the operation when the surgeons have finalised their use of the monitoring and the patients are still receiving total intravenous anaesthesia (propofol and remifentanil). If needed, each patient will be given 0.1mg /kg rocuronium to facilitate surgical closure. When the train of four count is of 2 or more the patients will be administered the cross-over drug (placebo if received sugammadex initially and vice versa) and the motor evoked potentials and same anaesthetic variables as above will be recorded for 3,6 and 9 minutes post cross-over dose.

8. Assessment

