A peripheral nerve monitor may be used to monitor the degree of residual neuromuscular blockade. This is standard anaesthetic equipment with the most common mode to assess residual blockade used being a train of four count. This involves adhesive dots applied over the ulna nerve and a current applied (approximately 70-80mA) in a train of four impulses 0.5 seconds apart with a pulse width of 250 microseconds. It is a safe method of assessing the occupancy of

acetylcholine receptors at the neuromuscular junction by observing the number of twitches displayed in the peripheral muscle (e.g thumb movement).

Number of twitches

- 0- 100% receptors blocked
- 1- 90% receptors blocked
- 2- 75-80% receptors blocked
- 3- 75% receptors blocked
- 4- 0% receptors blocked

For the purposes of our study we plan to continuously monitor the train of four count and ratio using a peripheral nerve stimulator module that is built into the anesthesia machine (GE Datex Ohmeda). The train of four count on both measuring tools will be delivered as a train of four impulses 0.5 seconds apart (2Hz) at 70-80mA with a pulse width of 250 microseconds.

Our current approach does not involve routine measurement of the degree of residual neuromuscular blockade with a peripheral nerve stimulator. This is a safe approach as monitoring is achievable with partial blockade but may not necessarily be most beneficial in patients with existing neurological impairment as complete reversal of neuromuscular blockade is not ensured.(Li, Song et al. 2010)

The issues with this current technique are;

- a) Patients cannot be monitored for neurological changes during their transfer into the prone position
- b) There is likely residual neuromuscular blockade decreasing the amplitude of motor evoked potentials

A cases series of 10 patients in healthy subjects undergoing lumbar spine surgery demonstrated a 74% increase in mean amplitude of the MEPs with reversal of neuromuscular blockade with sugammadex 2mg/kg.(Batistaki, Papadopoulos et al. 2012)

We plan to perform a randomised controlled cross over trial comparing the change in MEP amplitudes with administration of sugammadex or placebo. This will be performed on at risk patients (e.g. cervical myelopathy) undergoing posterior cervical spine surgery where MEPs can be more difficult to attain but of higher utility.(Kombos, Kopetsch et al. 2003)

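### The period-2 block that sugammadex is meant to reverse is not assured, and Section 11 names neither the period nor a paired analysis for the crossover

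*Combined protocol and SAP*

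**What the plan says.** **Washout.** Section 7.2: "A minimum washout period of 100 min after the last bolus dose of rocuronium (equivalent to 5 half-lives) is required". Recovery is then to be checked on a peripheral nerve stimulator by the absence of fade. Section 6.1 has the same rule. Both the interval and the check refer to rocuronium; neither refers to sugammadex, the drug being crossed over.

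**Entry to period 2.** Three places describe it.
- Crossover rationale, just before section 4: "When the patient returns to a train of four count of 2 or more on peripheral nerve monitor", MEPs are repeated and the other drug is given.
- Section 6.1: "After the preconditions are achieved on peripheral nerve stimulator or the direct train of four monitor, the second intervention" is given. No re-block is mentioned.
- Section 7.2: "If needed, each patient will be given 0.1mg /kg rocuronium to facilitate surgical closure". The second drug then follows at a TOFC of 2 or higher.

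**Meaning of the TOFC.** The Background scale gives "2- 75-80% receptors blocked" and, at the recovered end, "4- 0% receptors blocked".

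**Period 1.** Section 7.2 re-doses rocuronium before prone positioning if two or more twitches are present. It then takes baseline MEPs at a TOFC of 2 or higher; section 6.1 gives a count of exactly 2.

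**Outcome and analysis.** Section 6.1: "The primary outcome is the change of MEP amplitude of the first dorsal interossei from baseline 3 minutes after administration". Section 10.2 sizes the trial as a two-intervention crossover. Section 11 gives one Mann-Whitney U test of amplitude values between two groups, with no period, pairing or baseline stated.

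**The concern.** The hypothesis in section 4 is that reversing neuromuscular block raises MEP amplitude. Sugammadex given to a patient with no block cannot test it. The plan requires full recovery before period 2 and leaves re-block to surgical need, so two anaesthesiologists could both follow the protocol and run period 2 differently. A crossover estimate averages the two periods, and a period with little to reverse pulls a real effect down. A reader of the crossover result alone could not tell a weak drug effect from a period 2 that lacked block. Section 11 offers no protection, because it does not say which period or which within-patient comparison is tested.

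**Working it through.** **Inputs.** From section 10.2: difference 1200 microV, within-patient SD 1600 microV, two-sided 0.05, power 80%, 30 patients raised to 40. Assumed, because the documents give no values:
- bS and bP (0 to 1): the fraction of the period-1 block present at the second dose in sugammadex-first and placebo-first patients;
- g: the spontaneous 3-minute gain under placebo.

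**1. The plan's own figure.** N = 2 × [1600 × (1.960 + 0.842) / 1200]² = 27.9, or 28 by the normal approximation. By noncentral t with SD of difference 1600√2 = 2263, 30 patients give 80% power. Dropout: 30 / (1 − 0.25) = 40. The stated size reproduces, on the premise that the full 1200 applies in both periods.

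**2. Block at the second dose.** On the Background scale, a TOFC of 2 or higher spans 75-80% down to 0% of receptors blocked. A patient who passes the no-fade check and is not re-dosed sits at the 0% end.

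**3. Effect on the estimate.** Let B be the period-1 baseline and D = 1200 + g the gain when the full block is reversed.
- Period 1: sugammadex amplitude B + D, change D; placebo amplitude B + g, change g.
- Period 2, sugammadex-first (now placebo): baseline B + (1 − bS)D, change bS·g.
- Period 2, placebo-first (now sugammadex): baseline B + (1 − bP)D, change bP·D.

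Raw amplitude, sugammadex minus placebo: 1200·bS in sugammadex-first and 1200 in placebo-first, mean 600(1 + bS).

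Change from baseline: 1200 + g(1 − bS) and 1200·bP − g(1 − bP), mean 600(1 + bP) + g(bP − bS)/2.

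| Period-2 block | Raw amplitude | Change from baseline |
|---|---|---|
| Full in both (bS = bP = 1) | 1200 | 1200 |
| Half in both (0.5, 0.5) | 900 | 900 |
| None in either (0, 0) | 600 | 600 |
| Sugammadex-first not blocked (bS = 0, bP = 1) | 600 | 1200 + g/2 |
| Placebo-first not blocked (bS = 1, bP = 0) | 1200 | 600 − g/2 |

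A baseline-adjusted estimate equals the raw contrast if the baseline slope is 0 and the change contrast if it is 1. Only assured re-block in both sequences protects both scales.

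**4. Power of the crossover, 30 patients.**
- Raw amplitude (SD of difference 2263): 80% at 1200, 56% at 900, 29% at 600. With all 40 patients, 37% at 600.
- Difference of two change scores: four measurements with equal correlations (assumed) give variance 4 × 1600², SD 3200. Power is 51%, 32% and 17%.

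**5. Power of a period-1 comparison at 1200 microV, baseline-adjusted.** If 1600 is the within-patient SD and r the baseline-outcome correlation, total SD = 1600/√(1 − r) and residual SD = total × √(1 − r²) = 1600√(1 + r).
- r = 0.5: SD 1960; 47% with 20 v 20, 37% with 15 v 15.
- r = 0.7: SD 2086; 43% and 33%.

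**The case against.** **The sections can be read as one sequence:** recovery, then rocuronium, then TOFC returning to 2, then the drug. The rationale's wording points that way, and no re-block in either sequence is a worst case, not the evident intent. This stands as a reading, but section 7.2 makes the dose conditional on surgical need and section 6.1 omits it.

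**Period 1 has the same open threshold in section 7.2.** This stands, so the open threshold is not peculiar to period 2. In period 1, however, re-dosing before prone positioning tightens the block and randomisation balances what remains. Block in period 2 can depend on the first drug and on discretion at closure.

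**The two groups in Section 11 may be the randomised arms in period 1.** Section 10.2 does use group for the arms, and such a comparison would avoid the problem. Section 11 does not say so, and the sample size rests on within-patient pairing.

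**A reader might infer that the missing sugammadex washout by itself biases the primary outcome.** The documents do not support that. MEPs are recorded again before the second drug, and full one-sided carryover (bS = 0, bP = 1) leaves the change score at 1200 + g/2. Carryover would dilute a raw-amplitude contrast, but its size cannot be derived: the documents give no sugammadex half-life and do not say that it prevents re-block.

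**Conclusion.** The concern holds in this form: the plan does not assure a block to reverse in period 2, and Section 11 does not specify an analysis that matches the crossover or is protected from that gap. The estimate can fall from 1200 to as little as 600 microV. On the declared change outcome, with g ignored, the loss depends on re-block in placebo-first patients; on raw amplitude it depends on re-block in sugammadex-first patients. The raw-amplitude powers in step 4 should not be read across to the change score, which has its own lower set under equal correlations. All these figures are bounds, since no re-block rate is given. The sample size arithmetic is not in dispute. The absence of any sugammadex interval or check is a real gap in wording and reporting, but a secondary one. The point should be addressed, with medium confidence in its practical size.

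**What to change.** 1. **Primary analysis (Section 11).** Replace the unpaired Mann-Whitney test with a paired crossover model of 3-minute first dorsal interosseous amplitude, with treatment, period and sequence terms, adjusted for each period's own baseline. Designate it as primary.
2. **Supporting analysis.** Always report beside it, with a confidence interval, the baseline-adjusted period-1 comparison between the randomised groups. Use no preliminary carryover test.
3. **One entry condition for period 2**, stated alike in the crossover rationale and sections 6.1 and 7.2: after the no-fade check, give 0.1 mg/kg rocuronium, then take baseline MEPs and give the study drug when TOFC returns to 2. Section 6.1 already sets that target for period 1.
4. **Reporting and wording.** Report period-2 TOFC, baseline MEP, rocuronium re-dosing and the interval between study drugs by sequence. Reword sections 6.1 and 7.2 so that rocuronium recovery is not taken as sugammadex clearance.

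**Cost.** Items 1, 2 and 4 need wording, one derived interval and analyses of data already planned. Item 3 turns a discretionary dose into a protocol step; section 7.1 already recommends a train-of-four check, with reversal if appropriate, at the end of the case. The period-1 estimate will be imprecise, with power of about 33-47% if 1600 is the within-patient SD, which is why it supports the crossover model and does not replace it.
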